1.2 Study design

This is a 3-part study in patients with advanced solid tumours:

- Part A will determine the effect of food on the PK of olaparib and the effect of olaparib on the QT interval following a single oral dose of olaparib tablets;
- Part B will determine the effect of olaparib on the QT interval following multiple oral dosing of olaparib tablets;
- Part C will allow patients continued access to olaparib tablets after the PK and QT phases (Parts A & B) and will provide for additional safety data collection.

A total of 48 patients are planned to be enrolled at approximately 8 sites in Western Europe; approximately 42 evaluable patients will be expected to complete the study.

Part A of this study is a randomised, open-label, 2-treatment period crossover study in approximately 48 patients with advanced solid tumours. Each patient will receive a single oral dose of olaparib tablets 300 mg in each of 2 treatment periods (once in the overnight fasted state and once immediately following a high-fat meal at breakfast time), with at least 5 and no more than 14 days (washout) between doses. Digital ECG (dECG), PK assessments, and safety assessments will be obtained for up to 72 hours post-dose in each treatment period. Additionally, during the first treatment period, patients will undergo baseline dECG assessments on Day -1 (ie, the day prior to dosing) at clock times matched to planned/scheduled dECG assessment times on the dosing day (Day 1). Patients will check into the clinic on the evening of Day -2 (first treatment period) or the evening of Day -1 (second treatment period) and remain resident until 24 hours after each dose of olaparib tablets (Day 2). The dECGs performed on Day 1 in each treatment period will be clock-

matched to the actual times that the Day -1 dECGs are performed in the first treatment period. Patients will return to the clinic for assessments on Days 3 and 4 of each treatment period. On Day 1 of Part A patients should be fasted over the same time period as Day -1.

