Part B of this study is an open-label study in the same patients who participated in Part A. Upon completion of Part A, following a washout period (of at least 5 days and no more than 14 days between the last dose in Part A and Day -1 of Part B) and providing the patient continues to meet the study entry criteria, each patient will receive olaparib tablets 300 mg bd for 5 days. Patients will check into the clinic on the evening of Day -2. On Day -1, baseline dECG assessments will be performed at clock times matched to planned/scheduled dECG assessment times on Day 5. Patients will be discharged from the clinic on the evening of Day -1. Patients will self-administer their olaparib doses under fasted conditions (from 1 hour prior to 2 hours after the olaparib dose) from Day 1 up to the morning of Day 4 on an outpatient basis. On the evening of Day 4, patients will check back into the clinic, and will receive their Day 4 evening dose. On the morning of Day 5, patients will receive their Day 5 morning dose after an overnight fast and will remain fasting for 4 hours post-dose. Patients will undergo dECG and PK assessments pre-dose and for 12 hours post-dose. The dECGs performed on Day 5 will be clock-matched to the actual times that the Day -1 dECGs are performed. Patients will be discharged from the clinic after completing 12-hour assessments on Day 5, and will self-administer their evening Day 5 dose of olaparib tablets. On Day 5 of Part B patients should be fasted over the same time period as Day -1.

On completion of Part B, patients may be entered into Part C and continue to take olaparib tablets (300 mg bd) if they and the investigator agree that this is appropriate. Patients should start Part C immediately after the last dose received in Part B. Patients will have weekly clinic visits for the first 4 weeks; thereafter visits will be every 4 weeks. Part C will be of 12 months' duration from the date the last patient enters this part of the study.

During and after Part C, patients may continue to take olaparib tablets. After the end of Part C patients will be seen as per their normal routine clinical schedule and no clinical data will be collected, other than serious adverse events (SAEs) and drug dispensing/accountability.

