For change from baseline (time-matched day -1): Baseline for the PD data in Part A is defined as Day -1 of treatment period 1 in Part A, and baseline for the PD data in Part B is defined as Day -1 in Part B. For each patient, the change-from-baseline in a PD variable at each time point will be calculated as the difference between the mean of the replicate value at each post-dose time point and the mean of the time-matched replicate value at the corresponding baseline.

- Safety and tolerability will be assessed by:
 - Assessment of adverse events (AEs), graded by [CTCAE](#) (v4.03)
 - Physical examination
 - Vital signs (including BP and pulse)
 - Standard 12 lead ECGs
 - Evaluation of laboratory parameters (clinical chemistry, haematology, and urinalysis)

Adverse events (AEs) will be classified according to the terminology of Medical Dictionary for Regulatory Activities (MedDRA), Version 16. AEs will also be assigned a maximum CTC grade by the Investigator.

Each adverse event will be assigned to the period of the study in which they started as follows: The baseline period is the time between enrolment into the study and receipt of the first dose of study treatment. The treatment period is the time between receipt of the first dose of study drug and the follow-up assessment at the end of the study. The treatment period is divided into Part A, Part B and Part C, with Part A being subdivided according to which food condition study treatment was received under. AEs occurring in the baseline period will be listed only and will not be included in any summary tables.

Table 1 Adverse event occurrence

Adverse event occurrence	Period assigned	Study treatment (food condition)
Date and time before first treatment with olaparib	Baseline period	Not applicable
Date and time the same as or greater than the date and time of the first treatment with olaparib but before date and time of second treatment	Treatment period 1 (Part A)	Fed [OR] Fasted, dependent on treatment sequence
Date same as or greater than date of first treatment with olaparib but prior to date of second treatment; but time is missing	Treatment period 1 (Part A)	Fed [OR] Fasted, dependent on treatment sequence

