Date and time the same as or greater than the date and time of the second treatment with olaparib, but prior to the date and time of Part B treatment, or up to (and including) 30 days after the last dose date (where the patient does not enter Part B)	Treatment period 2 (Part A)	Fed [OR] Fasted, dependent on treatment sequence
Date same as or greater than date of second treatment with olaparib, but prior to the date and time of first Part B treatment, or up to (and including) 30 days after the last dose date (where the patient does not enter Part B); but time is missing	Treatment period 2 (Part A)	Fed [OR] Fasted, dependent on treatment sequence
Date and time the same as or greater than the date and time of the first Part B treatment with olaparib, but prior to the date of optional Part C treatment, or up to (and including) 30 days after the last dose date (where the patient does not enter Part C)	Part B	Olaparib 300 mg bd
Date same as or greater than date and time of first Part B treatment with olaparib, but prior to the date of optional Part C treatment, or up to (and including) 30 days after the last dose date (where the patient does not enter Part C); but time is missing	Part B	Olaparib 300 mg bd
Date same as or greater than start date of optional Part C treatment with olaparib (time not recorded in Part C), up to (and including) 30 days after the last dose date	Part C	Olaparib

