4.2.5 Safety parameters (Parts A & B, and Part C)

Safety variables

All safety analyses will be performed on the safety analysis set.

Where more than one measurement was made at baseline, the last non-missing pre-dose value will be taken as the baseline measurement.

If the baseline measurement is missing then the last non-missing pre-dose value will be taken as baseline.

Treatment exposure

Treatment exposure data will be collected for patients in Parts B and C. For Part B the mean daily dose will be summarised. For Part C the duration of treatment exposure, dose interruptions and reductions, mean daily dose and adherence will be summarised and listed.

Adverse events

All AEs will be listed for each patient, and will be summarised for Parts A & B, and separately for Part C of the study. In addition, the following summary tables will be presented by treatment (food condition (Part A) and olaparib 300 mg bd (Part B)) and across all patients for Part A, and across all patients only for Part C.

- Summary of number (%) of patients who had at least one adverse event in any category (Any AE, any causally related AE, any AE of CTCAE grade 3 or higher, any causally related AE of CTCAE grade 3 or higher, any AE with outcome = death, any causally related AE with outcome=death, any SAE (including events with outcome = death), any causally related SAE (including events with outcome = death), any SAE causing discontinuation of IP, any causally related SAE causing discontinuation of IP, any AE leading to discontinuation of IP, any causally related

AE leading to discontinuation of IP, any other significant AE, any other causally related significant AE).

- In addition, a summary of number (%) of AEs in any category (episode level) will also be presented.
- Summary of number (%) of patients who had at least 1 AE by preferred term, arranged by system organ class.
- Summary of number (%) of patients who had at least 1 AE by system organ class and preferred term presented by maximum reported CTCAE grade.
- Summary of number (%) of patients who had at least 1 olaparib/other causally related AE by preferred term.
- Summary of number (%) of patients who died, summary of number (%) of patients with an AE with outcome = death. In addition, a listing of deaths, and a listing of key information for AEs with outcome = death will be presented .
- Summary of SAEs (episode level) by preferred term, arranged by system organ class.

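### Part A and Part B adverse event percentages rest on unequal collection windows, and the Part B window depends on who enters Part C, so the two cannot be read against each other

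*SAP*

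**What the plan says.** **Windows (SAP section 3, Table 1, with section 1.2).**
- Part A period 1 runs from the first dose, "but before date and time of second treatment". Section 1.2 sets the gap: "with at least 5 and no more than 14 days (washout) between doses".
- Part A period 2 runs to the first Part B dose, "or up to (and including) 30 days after the last dose date (where the patient does not enter Part B". The gap before Part B is "of at least 5 days and no more than 14 days between the last dose in Part A and Day -1 of Part B".
- In Part B, "each patient will receive olaparib tablets 300 mg bd for 5 days". Its AE window ends before the date of Part C treatment, "or up to (and including) 30 days after the last dose date (where the patient does not enter Part C". Section 1.2 adds: "Patients should start Part C immediately after the last dose received in Part B".

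**Tables (section 4.2.5).** For the AE displays, "the following summary tables will be presented by treatment (food condition (Part A) and olaparib 300 mg bd (Part B". The entries are numbers and percentages of patients with at least one event, plus event counts. Neither a common onset window nor an exposure-adjusted rate is planned.

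**Exposure (sections 4.1 and 4.2.5).** Treatment duration is summarised for Part C only, and for Part B only mean daily dose is summarised. No planned table shows how long each Part A or Part B column was observed. Part C is reported later, in a separate study report.

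**The concern.** Patients with advanced solid tumours can have AEs from their disease whatever the drug does, so the share with at least one event rises with the length of observation. Here the length differs between the Part A columns and the Part B column. Within Part B it also differs about sevenfold (35/5) between patients who stop and patients who go on to Part C. Going on is a decision by patient and investigator taken around the end of Part B, and tolerability may influence it.

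Safety and tolerability is a stated secondary objective. A reader who sees single-dose and twice-daily columns in one layout will compare them. The comparison could show a difference where the event rate is the same, or hide one where it is not, and nothing in the planned output lets the reader correct for it.

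**Working it through.** The plan states no AE rate, continuation proportion or mean window, so there is no figure of its own to reproduce here. The window lengths follow from the document; the rates and continuation proportions are assumptions, shown as ranges.

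**Step 1. Window lengths**

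| Column part | Patient continues | Patient does not continue |
|---|---|---|
| Part A period 1 | 5-14 days | no end stated |
| Part A period 2 | (5-14) + 1 = 6-15 days | dose day + 30 = 31 calendar days |
| Part B | 5 days | 5 + 30 = 35 calendar days |

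The extra day in period 2 is the step from Day -1 to Day 1 of Part B. The calculation assumes that every Part A patient receives both doses. Mid-washout values are 9.5 days for period 1 and 10.5 days for period 2.

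**Step 2. Fed versus Fasted**

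Each food condition is given in period 1 in one sequence and in period 2 in the other. With balanced sequences, both columns have the same expected mean window:
- all enter Part B: (9.5 + 10.5)/2 = 10.0 days each
- 12.5% do not enter Part B: period 2 = 0.875 × 10.5 + 0.125 × 31 = 13.06 days, and (9.5 + 13.06)/2 = 11.3 days each

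Only a chance imbalance between sequences separates them. If 6 of 48 patients do not enter Part B and the rate is 0.05 per day, the columns differ by 0 points for a 3:3 split, 1.6 for 4:2 and at most 4.7 for 6:0 (probability about 2%, both directions together).

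**Step 3. Part A versus Part B with the same rate everywhere**

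P(at least one AE in d days) = F(d) = 1 − exp(−rate × d). Let q be the proportion not entering Part B and r the proportion not entering Part C.
- Part A (Fed = Fasted) = ½ F(9.5) + ½ [(1 − q) F(10.5) + q F(31)]
- Part B = (1 − r) F(5) + r F(35)

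At 0.05 per day: F(5) = 22.1%, F(9.5) = 37.8%, F(10.5) = 40.8%, F(31) = 78.8%, F(35) = 82.6%.

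| Rate per day | All continue (A vs B) | q = r = 12.5% | q = 12.5%, r = 50% |
|---|---|---|---|
| 0.02 | 18.1% vs 9.5% | 19.8% vs 14.6% | 19.8% vs 29.9% |
| 0.05 | 39.3% vs 22.1% | 41.7% vs 29.7% | 41.7% vs 52.4% |
| 0.10 | 63.2% vs 39.3% | 65.1% vs 46.6% | 65.1% vs 68.2% |

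**Step 4. Where the direction changes**

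If all enter Part B, the columns are equal when F(5) + r [F(35) − F(5)] equals the Part A value. At 0.05 per day, r = (39.3 − 22.1)/(82.6 − 22.1) = 28%. The same sum gives 21% at 0.02 per day and 41% at 0.10. Below that proportion Part B looks better than Part A, and above it worse, with no difference in event rate.

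Over the scenarios tried (0-25% not entering Part B, 0-50% not entering Part C, shortest to longest washout), the ratio of mean windows, Part B to Part A, runs from about 0.3 to 3.6.

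**Step 5. With a common window**

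Five days in every column at 0.05 per day gives 22.1% in Fed, Fasted and Part B alike. Equal rates then give equal percentages.

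**The case against.** Assigning events by period of onset is a normal choice for descriptive tables. The objective is to assess safety and tolerability, not to contrast single with repeated dosing, and no test or between-column statement is planned. All events are listed by patient, and separate summaries of causally related events partly deal with background disease. Part B always follows Part A in the same patients, so the contrast is confounded with order and calendar time whatever the window. Observation differs too: in Part A patients are resident to 24 hours and attend on Days 3 and 4, while in Part B they are outpatients from Day 1 until the evening of Day 4.

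All of this stands, and it limits the point to a reporting improvement. It does not remove it. The Part B percentage still mixes 5-day and 35-day windows in unknown proportion, and no planned table reveals the mix.

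Three stronger readings are tempting and are not supported:
- *Fed and Fasted differ by construction.* The 30-day tail belongs to period 2, not to a food condition, and the randomised crossover spreads it over both columns.
- *The layout is always biased against the single-dose columns.* The direction depends on the continuation rate, which the SAP does not give.
- *Columns could differ as widely as 22% and 83%.* Those values, at 0.05 per day, apply to single patients with 5-day and 35-day windows. Column percentages average over patients and lie closer together.

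**Conclusion.** The point holds for Part A versus Part B only. Table 1 and section 4.2.5 together produce a Part B percentage that depends on how many patients enter Part C and that is not comparable with the Part A columns. At the same underlying rate, the artefact is about 9 to 24 percentage points in favour of Part B if everyone continues (18.1% vs 9.5% at 0.02 per day; 63.2% vs 39.3% at 0.10). It runs about 3 to 11 points the other way if 12.5% skip Part B and 50% skip Part C.

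The unequal windows come from the document. The sizes rest on assumptions: a constant rate, equal in every column, of 0.02 to 0.10 per day; mid-washout gaps; balanced sequences; and the continuation proportions shown. The primary food-effect analysis is untouched. This is a worthwhile and inexpensive improvement to descriptive safety tables.

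**What to change.** In section 4.2.5:
1. Add the AE overview and the system organ class/preferred term tables for Fed (A), Fasted (A) and 300 mg bd (B), restricted to events with onset on calendar Days 1-5 of each period.
2. Report total patient-days at risk for each column. For this, state when period 1 ends for a patient who receives no second dose, which Table 1 leaves open.
3. Base any Part A versus Part B statement on the Day 1-5 tables.
4. Keep the full Table 1 assignment as the all-AE display.

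The window should be in calendar days rather than 120 hours. Table 1 cuts Part B at the Part C date, which can fall short of 120 hours after the first Part B dose, and it allows for missing onset times. Doses in Part A are at least 5 days apart and Part B dosing lasts 5 days, so Days 1-5 exist in every period.

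The cost is SAP wording and a few extra tables from data already collected. Later-onset events would appear only in the full-window display. The Part A versus Part B contrast would remain descriptive, and confounded with order and with differing clinic observation.

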4. ANALYSIS METHODS

4.1 General principles

Statistical summaries and analyses will be performed by Quintiles under the direction of the Biostatistics Group, AstraZeneca using SAS® version 8.1 or higher and, where appropriate, additional validated software.

After the last patient has completed the treatment period in Part B, the database for Parts A & B of the study will be locked and the data will be reported in a Part A and Part B CSR. AstraZeneca anticipates receiving regulatory questions relating to QT effect of olaparib in relation to a marketing authorisation application. In the event that Part A and Part B are not completed at the time of receipt of the questions, an analysis of the available Part A and Part B data may be performed to enable AstraZeneca to respond within the permitted time frame. On completion of Part C, a further database lock will occur and the Part C data will be reported in a separate Part C CSR.

All individual data as recorded in the final study database will be provided by Quintiles Data Management.

The treatments will be labelled in all summaries and listings as:

- “Fasted (A)”
- “Fed (A)”
- “Olaparib 300 mg bd (B)”
- “Olaparib 300 mg bd (C)”

and defined as follows:

- Fasted: Olaparib 300 mg (2x150 mg tablets) administered in fasted state (Part A).
- Fed: Olaparib 300 mg (2x150 mg tablets) administered in fed state following high-fat meal (Part A).
- Olaparib 300 mg bd: Olaparib 300 mg (2x150 mg tablets) twice daily for 5 days (Part B).
- Olaparib 300 mg bd: Olaparib 300 mg (2x150 mg tablets) twice daily (Part C).

The 2 treatment sequences, to which patients will be randomised in Part A, will be labelled as:

- “Fed/Fasted (A)”
- “Fasted/Fed (A)”

and defined as follows:

- Fed/Fasted: Olaparib 300 mg (2x150mg tablets) administered in high-fat fed state in period 1 and in fasted state in period 2.
- Fasted/Fed: Olaparib 300 mg (2x150mg tablets) administered in fasted state in period 1 and in high-fat fed state in period 2.

The number of patients screened and included in the safety analysis set will be summarised. Demographic and baseline characteristics will be summarised and listed for the safety analysis set.

For qualitative demographic and safety variables, the population size (N for sample size and n for available data) and the percentage (of available data) for each class of the variable will be presented.

Quantitative demographic and safety variables will be summarised using descriptive statistics, including n, mean, SD, median, minimum, and maximum values. Where appropriate, assessments will be summarised by visit.

Treatment duration will be summarised for Part C only. Treatment duration is based on the dates of first and last dose relating to Part C.

Study day will be calculated as follows:

- Days prior to first dose: Study day=date – first dose date.
- Days on or after first dose: Study day=date – first dose date+1.

Where date is missing, but is required in the calculation of *time to randomisation*, date will be imputed as 01 i.e. 1st of the month. Otherwise no imputations will be made for any missing data, unless agreed by the study team.

Quantitative PK variables will be summarised using descriptive statistics, including n, arithmetic mean, SD, coefficient of variation (%CV), median, minimum, and maximum values. Additionally, geometric means and geometric %CV (%GCV) will be reported as described in [Table 2](#). The geometric mean is calculated as the exponential of the arithmetic mean calculated from data on a log scale. The %GCV is calculated as $100 \cdot \sqrt{(\exp(s^2) - 1)}$ where s is the SD of the data on a log scale. Mean, SD, %CV, geometric mean, and %GCV will not be calculated for t_{\max} ; t_{\max} will be summarised by median, minimum and maximum.

For all PK data, descriptive statistics will follow the rounding conventions described in [Table 2](#). Coefficients of variation (%CV and %GCV) will always be reported to 1 decimal place. Ratios and any corresponding confidence intervals (CIs) that are obtained during inferential statistical analysis shall be reported to 2 decimal places.

The plasma concentrations will be reported to the same precision as the source data.

Table 2 Reporting accuracy of pharmacokinetic data

Variable / Parameter	Data	Mean	SD	%CV & %GCV	Median	Min	Max	Differences/ Ratios & CIs
Plasma concentrations	As reported	+1sf	+1sf	1dp	+1sf	3sf	3sf	
Single dose parameters								
C _{max}	As reported	+1sf	+1sf	1dp	+1sf	3sf	3sf	2dp
t _{max}	As reported	NA	NA	NA	2dp	2dp	2dp	2dp
AUC	3sf	4sf	4sf	1dp	4sf	3sf	3sf	2dp
AUC _{0-t}	3sf	4sf	4sf	1dp	4sf	3sf	3sf	2dp
CL/F	3sf	4sf	4sf	1dp	4sf	3sf	3sf	
Vz/F	3sf	4sf	4sf	1dp	4sf	3sf	3sf	
t _{half}	3sf	4sf	4sf	1dp	4sf	3sf	3sf	
lamdaz	4sf	5sf	5sf	1dp	5sf	3sf	3sf	
Multiple dose (steady state) parameters								
C _{ss,max}	As reported	+1sf	+1sf	1dp	+1sf	3sf	3sf	
t _{ss,max}	As reported	NA	NA	NA	2dp	2dp	2dp	
C _{ss,min}	As reported	+1sf	+1sf	1dp	+1sf	3sf	3sf	
t _{ss,min}	As reported	NA	NA	NA	2dp	2dp	2dp	
C _{ss,avg}	As reported	+1sf	+1sf	1dp	+1sf	3sf	3sf	
AUC _{0-τ}	3sf	4sf	4sf	1dp	4sf	3sf	3sf	
FI	0dp	1dp	NA	NA	NA	1dp	1dp	
CL _{ss} /F	3sf	4sf	4sf	1dp	4sf	3sf	3sf	

sf Significant figures.

dp Decimal places.

For descriptive statistics of concentrations, non-quantifiable (NQ) values of plasma concentrations will be handled as follows:

- If, at a given time point, 50% or less of the plasma concentrations are NQ, the mean, SD, geometric mean, %CV, and %GCV will be calculated by substituting the limit of quantification (LOQ) for values which are NQ.
 - olaparib: use low range LOQ = 0.0005 µg/ml
- If more than 50%, but not all, of the concentrations are NQ, the mean, geometric mean, SD, %CV, and %GCV will be reported as not calculable (NC).

- If all the concentrations are NQ, the geometric mean and mean will be reported as NQ and the SD, %CV, and %GCV as NC.

The PK parameters will be reported as described in [Table 2](#).

The PK data will be presented by treatment for Part A (food condition) and Part B (olaparib 300 mg bd).

The PD analysis (QT/QTc interval analysis) and the PD summaries, figures, and data listings will be the responsibility of the Quintiles biostatistician.

Additionally, dECG data from this study will be pooled with data from another study(ies). The methodology will be described separately, and the data analysed separately by AstraZeneca using statistical methods and PK/PD modeling.

